1.0 Research Design

1.1 Purpose/Specific Aims

The primary purpose of this study is to compare the effectiveness of a usual care (UC) vs. targeted generic print (TP) vs. tailored telephone counseling and navigation intervention (TCN) on cancer genetic risk assessment (CGRA) uptake at 6 months for hereditary breast and ovarian cancer (HBOC). Secondary purposes are: 1) to compare the effectiveness of a TP vs. a TCN intervention vs. UC on CGRA uptake at 12 months, after removal of key access barriers; 2) to compare uptake of genetic testing for HBOC across the three study arms at 6 and 12 months; 3) to compare cognitive (beliefs, attitudes, and knowledge) and affective (distress, stress, fear) intermediate endpoints among women in the three study arms and explore potential underlying theoretical mediating and moderating mechanisms that will further specify and elucidate significant intervention effects; and 4) to perform an economic evaluation alongside this randomized controlled trial to estimate the cost effectiveness of the two interventions compared to each other and usual care, for uptake of CGRA services from the societal and payer perspectives.

The New Jersey State Cancer Registry (NJSCR) will collaborate with investigators from the state cancer registries of Colorado and New Mexico ([name] = overall Principal Investigator) to identify women recently diagnosed with high-risk breast and ovarian cancer. The NJSCR will (a) recruit and consent New Jersey patients who are eligible to participate in the study, and (b) securely send contact and cancer-related information to the overall PI for women who consent so that they can be enrolled onto study by the overall PI. This application is for case ascertainment using the NJCSR.

A. Objectives

AIM 1: Compare the effectiveness of a TP vs. a TCN intervention vs. UC on CGRA uptake 6 months (primary outcome) after the intervention and at 12 months, after removal of key access barriers.

AIM 2: Compare uptake of genetic testing for HBOC across the three study arms at 6 and 12 months.

AIM 3: Compare cognitive (beliefs, attitudes, and knowledge) and affective (distress, stress, fear) intermediate endpoints among women in the three study arms and explore potential underlying theoretical mediating and moderating mechanisms that will further specify and elucidate significant intervention effects.

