NJSCR contracted with Salt City Research to design a tracking tool for patient contact studies, particularly mail and phone contact, and participant response status. CRIMSON works with SEER*DMS (NJSCR registry database system) and includes modifiable reports and tracking for mode of contact. Key features of CRIMSON include: (1) enhanced report functions and data collection for key recruitment statistics across all studies; (2) enhanced interoperability with SEER*DMS to reduce manual entry of data and improve data sharing; (3) improved data integrity, quality, consistency, and collection through implementation of validation tools and triggers, elimination of data redundancies, and execution of auto-fill and auto-coding of key variables to remove manual entry of data whenever possible; and (4) implementation of relational structure of the data system allowing for all studies and associated administrative data to be housed within a single data system.

After consent / “Agreement to Participate”, NJSCR staff will transfer data securely for consented individuals to the prime site for enrollment and participation in the study.

Briefly, the prime site will randomize the individuals into one of three study arms. NJSCR will not be involved in the intervention. Women will be randomized to one of three study arms: UC, mailed TP, and TCN delivered by a health education specialist. Group assignment will occur at the end of the baseline interview using a computerized randomized list. The interventions will take place ideally within 2 weeks but no more than 30 days upon completion of the baseline survey. Follow-up surveys will be conducted 1 month (to assess mediation), 6 months, and 12 months after randomization for the UC arm, and 1 month, 6 months, and 12 months after the interventions for TP and TCN arms. During the 6 and 12 month surveys, participants will be asked if they'd like to participate in future research. All survey questions will be stored in the REDCap database. The 3 arms will be compared with regard to uptake of CGRA at 6 months (primary outcome) and 12 months, and secondary outcomes including psychosocial and decision-making factors, CGRA preferences, genetic test uptake at 6 and 12 months, and cost outcomes at 6 and 12 months.

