1.8 Interviews, Focus Groups, Surveys, and/or Observations

A. Administration

NJSCR SITE:

Recently diagnosed cases will be identified by staff at the NJSCR and reviewed by a Certified Tumor Registrar for study eligibility. We will update address information for the case and the physician of record. Each person will be assigned an arbitrary study ID and imported into the study tracking database “CRIMSoN.” NJSCR staff will send a letter to the patient’s diagnosing physician of record to notify the physician that his/her patient is eligible for participation in the study. Two weeks after the physician letter is mailed, NJSCR staff will send the eligible patient a packet of study materials. One week (or five business days) after the initial mailing, staff at the NJSCR will conduct six to eight follow-up phone calls at varying times of the day and different days of the week. Those reached by phone will be given the option to provide a verbal consent to be contacted, which will be recorded in the tracking database. A Spanish-speaking NJSCR staff member will contact individuals who indicated Spanish as a preferred language during patient contact. NJSCR will track all contact with the patient using the CRIMSoN tracking database. After consent / “Agreement to Participate”, NJSCR staff will transfer data securely for consented individuals to the prime site for enrollment and participation in the study.

PRINCIPAL INVESTIGATOR SITE:

All interventions and surveys will be conducted by the Principal Investigator at the prime site. Women will be randomized to one of three study arms: UC, mailed TP, and TCN delivered by a health education specialist. Group assignment will occur at the end of the baseline interview using a computerized randomized list.

Timing and Frequency

The overall order of events for the study are in Table 4. NJSCR is responsible for recruiting cases.

Table 4: Study Timeline

Who	Task	Timeline		
NJSCR	Recruitment and Consenting	Start - Up Phase August 2018		
PI	Enrollment, Baseline Survey & Randomization	Baseline		
PI	Intervention	14-30 days post-baseline		
PI	Follow up surveys	Arm 1: Usual Care (UC)	Arm 2: Targeted Mailed Print (TP)	Arm 3: Telephone Counseling & Navigation (TCN)
PI	1 month	30 d > randomization	30 d > intervention	30 d > intervention
PI	6 months	180 d > randomization	180 d > intervention	180 d > intervention
PI	12 months	360 d > randomization	360 d > intervention	360 d > intervention

▪ Location

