All recruitment materials, surveys, and intervention materials will be available to participants in English or Spanish, depending on their preference. The TCN session will be conducted in English or Spanish, depending on the participant's preference. Spanish materials will be submitted to the IRB after the English materials have been approved. To further facilitate communication, Spanish speaking participants and study staff may use over the phone translation services.

There will be 4 surveys over the course of the study period (baseline, 1 m, 6m, 12 m) and will include different components as described below. These are developed at the prime site.

CGRA Decision and Genetic Test Uptake: Participants who have CGRA within 6 months of the intervention (or baseline survey for UC arm) will be considered “completers” of CGRA for the primary outcome. The primary outcome is medical record verified CGRA delivered by the 6-month follow-up. Those reporting that they had CGRA will be asked to sign a medical release form so that we may verify their self-reported CGRA. This approach is extremely feasible and has been successful in ours^{41,134} and others^{135,136} prior work. We will track the type of provider (e.g., physician, genetic counselor, etc.) who provided CGRA and document their genetics training via the documentation form. Using the same strategy, we will assess CGRA utilization at 12 months. Through the medical record release signed by patients, self-reported genetic testing (including type of test and test result) will also be medical record verified at 6 and 12 months.

Sociocultural Factors and Cues to Action: 1) Sociodemographics: age, gender, education, household income, financial status, marital status, rural-urban community area code,¹³⁷ living biological children, and health insurance status, country of origin, years lived in the U.S; 2) Medical history: personal/family history of cancer, cancer stage, health status, co-morbidity index; 3) Acculturation: Short Acculturation Scale;¹³⁸ 4) Family and friends social support and encouragement to obtain CGRA;^{41,139,140} 5) Family orientation: The Familism Scale;¹⁴¹ 6) Brief Fatalism Scale;^{142,143} 7) Health System Distrust;¹⁴⁴ 8) Receipt of a physician/provider recommendation for CGRA; and 9) Primary health care provider received tailored letter in the TPN arm.

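### The 6-month CGRA window starts at randomisation in UC but at delivery, up to 30 days later, in TP and TCN, and the handling of CGRA before delivery is not stated

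*Protocol*

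**What the plan says.** **Time zero.** Protocol section 1.3 places randomisation at baseline: "Group assignment will occur at the end of the baseline interview using a computerized randomized list". For UC, baseline and randomisation are therefore the same moment.

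**Start of the window.** Section 1.8.B (CGRA Decision and Genetic Test Uptake) states: "Participants who have CGRA within 6 months of the intervention (or baseline survey for UC arm) will be considered" completers. Aim 1 in section 1.1 also anchors on delivery: "CGRA uptake 6 months (primary outcome) after the intervention and at 12 months".

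**End of the window.** Section 1.8.B continues: "The primary outcome is medical record verified CGRA delivered by the 6-month follow-up". The survey clocks split in the same way. Section 1.3 sets surveys at 1, 6 and "12 months after randomization for the UC arm, and 1 month, 6 months, and 12 months after the interventions for TP and TCN arms". Table 4 in section 1.8.A gives the UC 6-month survey as "180 d > randomization" and counts the same 180 days from the intervention in TP and TCN.

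**Delivery.** Section 1.3 allows delivery "ideally within 2 weeks but no more than 30 days upon completion of the baseline survey". Table 4 says "14-30 days post-baseline". Section 1.6.A gives two weeks for the TP mailing and one month for the TCN call.

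**SAP.** Item 2 names TCN vs UC and TCN vs TP as the primary contrasts, on an intent-to-treat basis, and gives the 6-month window no origin. Item 4 starts the 12-month Kaplan-Meier curves at the intervention and gives UC no origin.

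**The concern.** Randomisation makes the arms comparable from the moment of assignment. Here the clock in two arms starts at an event after assignment, and in the third arm at assignment itself. Two rules that would settle the effect of this are not stated in these documents:

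1. Whether CGRA obtained between randomisation and delivery counts in TP and TCN. The first sentence in section 1.8.B suggests a start at delivery. The second fixes only an end.
2. Which window applies, under intent-to-treat, to a TP or TCN woman who never receives the intervention. A mailing date should normally exist in TP, so this concerns mainly TCN women who are not reached by phone.

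Under the inclusive reading, TP and TCN accrue events for longer after randomisation than UC, which favours them whatever the shape of the hazard. Under the exclusive reading, the windows are equal in length but cover different days. The primary count can therefore be derived in more than one way from the same records.

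**Working it through.** **Inputs.** From Protocol section 6.1.B: UC uptake of at most 7% by 6 months; 182 per arm; UC vs TP with a 15-point difference at alpha 0.017; TP vs TCN 19% vs 34% at alpha 0.025. From SAP item 2: 3% in UC or TP, 212 per arm, 2.5% per comparison. From sections 1.3, 1.6.A and Table 4: delays of up to 14 or 30 days. The documents give neither actual delays nor a hazard shape, so both are assumed and varied.

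**Test.** Two-sided normal test of two proportions with n per arm. With s0 = √(2p̄(1−p̄)/n) and s1 = √((p1(1−p1)+p2(1−p2))/n), the rejection probability is Φ((|p2−p1|−z·s0)/s1) + Φ((−|p2−p1|−z·s0)/s1).

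**The plan's own figures.** 7% vs 22%, n = 182, alpha 0.017 gives 95.7%. 19% vs 34%, n = 182, alpha 0.025 gives 84.5%. Both reproduce.

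**Length of the window.** From randomisation: 180 days in UC, up to 180 + 30 = 210 in TCN. 210/180 = 1.17, so up to 17% more time.

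**(a) All CGRA up to follow-up counts, no true effect.** Constant hazard h = −ln(1−p)/180; uptake at delay d is 1 − exp(−h(180+d)). For p = 0.07, h = 0.000403 per day. Rejection is for the contrast with UC at nominal 2.5%.

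| UC rate, n per arm | Delay | TP/TCN rate | OR | Rejection |
|---|---|---|---|---|
| 7%, 182 | 14 days | 7.5% | 1.08 | 2.8% |
| 7%, 182 | 30 days | 8.1% | 1.17 | 3.7% |
| 7%, 182 | uniform 0-30 days | 7.6% | 1.09 | 2.8% |
| 3%, 212 | 14 days | 3.2% | 1.08 | 2.6% |
| 3%, 212 | 30 days | 3.5% | 1.17 | 3.1% |

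Hazard shape: with S(t) = exp(−λt^k) fixed at 7% by day 180 and every woman delayed 30 days, k = 0.5 gives 7.5% (OR 1.08) and k = 2 gives 9.4% (OR 1.38, rejection 8.1%). The shift is always upward.

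**(b) CGRA before delivery excluded, no true effect.** Uptake is S(d) − S(180+d). At 7% and 30 days:
- k = 0.5: 4.6%, −2.4 points, OR 0.64
- k = 1: 6.9%, −0.1 point, OR 0.99
- k = 2: 9.2%, +2.2 points, OR 1.35

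**TCN vs TP.** Both arms use the same anchor, so only a difference in delay matters. Under (a) with TP at day 14 and TCN at day 30, the rates are 7.5% and 8.1%: OR 1.09, rejection 2.8%. With equal delays there is no bias.

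**Power of a day-180 count from randomisation.** Assume the UC hazard before delivery and the planned hazard after it: 1 − exp(−h_UC·d − h_TP(180−d)). For TP planned at 22%, this is 20.9% at d = 14 and 19.7% at d = 30. UC vs TP power at alpha 0.017 falls from 95.7% to 93.0% or 88.3%.

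**The case against.** **Anchoring on the intervention is a choice, not a slip.** Aim 1 says so, and sections 1.3, 1.8.A and 1.8.B apply it consistently, with 180 days from each arm's own start. This stands. A reader might infer that the anchoring is itself an error, or that the two sentences in section 1.8.B contradict each other. They do not: both end on the day of the 6-month follow-up. Only the treatment of the days before delivery is open.

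**The bias is small and the largest figures are upper bounds.** This stands too. The 30-day rows assume that every woman waits the maximum, while section 1.3 aims for two weeks. Seven per cent is the protocol's ceiling for UC. Nothing in the documents supports a hazard shape of 2. Uniform delays give OR 1.09, against the SAP's minimum detectable OR of 1.86.

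**Re-anchoring the primary outcome would cost more than it gains.** Under a constant hazard, TCN vs TP power would fall from 84.5% to 80.7% with both arms at day 14. It would fall to 66.9% in the extreme case of TP at day 14 and every TCN call at day 30. That is a poor exchange for removing about 1 point of bias, and it supports a sensitivity analysis instead.

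**The rules may exist elsewhere.** The protocol covers the New Jersey work and describes the prime site's procedures briefly; the SAP consists of methods text from five publications. A reader might infer that the trial had no rule. The documents support only that none is stated in them.

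None of this answers the two open questions, or gives the intent-to-treat comparison with UC a common time zero.

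**Conclusion.** The point holds as a cheap improvement and a gap in definition. The clocks differ by arm, by up to 30 days, and these documents do not settle how CGRA before delivery or a woman never treated is handled.

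With no true effect and a constant hazard, the inclusive reading adds 0.5 to 1.1 points to 7% for delays of 14-30 days. The exclusive reading changes it by about −0.1 point at 30 days. With other hazard shapes, the inclusive reading still favours TP and TCN, and the exclusive reading can move either way. The effect falls mainly on the UC contrasts, of which TCN vs UC is primary in the SAP.

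A reader might infer that the unequal window could produce the intervention effect by itself. The figures do not support that: about 1 point, or 2.4 points in the most extreme shape shown, is small beside 12-15 planned. What it can do is shift the reported odds ratio and leave the primary count open to two derivations. All sizes rest on assumed delays and hazard shapes.

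**What to change.** 1. Keep the intervention-anchored primary outcome of Aim 1. In its definition, state whether CGRA between randomisation and delivery counts, and give TP and TCN women who never receive the intervention the randomisation clock.
2. Add a sensitivity analysis of all randomised women that counts record-verified CGRA dated from randomisation to day 180 after randomisation in every arm, including CGRA before delivery.
3. Use randomisation as the common origin for the 12-month Kaplan-Meier curves, or report that version alongside.
4. Reconcile the delivery timings in section 1.3, section 1.6.A (Arms 2 and 3) and Table 4.

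**Cost.** Some wording and a re-derivation from event dates that the Kaplan-Meier analysis already needs. The TP and TCN 6-month surveys fall at or after day 180 from randomisation, so treated women need no new contact. The downside to disclose is that TP and TCN have less time after delivery in this analysis, so its estimates and power are somewhat lower (the UC vs TP figures above). A common day-210 window would avoid that loss, but it would count UC events after the 6-month offer to cover CGRA costs (sections 4.7.D and 6.1.A).

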Arm 3 - Telephone Counseling & Navigation: Within one month of the baseline survey, a bilingual health education specialists will conduct a 30-45 minute (depending on participant needs) telephone health education and counseling session with women randomized to this arm. The intervention will be offered in English or Spanish, depending on the participant's preference. Because theoretically-based tailored messages are generally more effective than generic messages in producing behavioral change,^{91,120} we will individualize the psycho-education and navigation session according to each participant's perceptions of threat and efficacy as derived from the EPPM,^{41,100} and according to personal factors such as HBOC and CGRA awareness, family history, cultural factors (e.g., ethnicity, language preference, familism, fatalism, family history), psychological and logistical concerns, knowledge, and barriers to CGRA that arise during the phone call. Prior to the telephone session, participants will receive the same brochure that the TP arm receives. After the phone call, participants will receive a tailored follow-up letter. It will include images tailored to the individual's age, self-identified ethnicity, and family composition. Health education specialists will enter this into the study database using user-friendly study-specific computer screens similar to our previous work.^{41,100} The Michigan Tailoring System (MTS), a publicly available software program, will be used to individually tailor messages and images using demographic, clinical and patient-reported data (<http://chcr.umich.edu/mts/>) for the letter. This information will be derived from the cancer registry data (age, type of cancer diagnoses) and during the survey or phone call (ethnicity, family history, primary care provider (which may be an oncology specialist), threat and efficacy appraisals, concerns (e.g., family member's risk and/or risk of second cancer, family orientation), top two CGRA facilitators/benefits and top two barriers, and action plan).

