Emotions: 1) Fear of HBOC risk (self, family): Affect in Risk Scale;^{145,163,164} 2) Cancer Worry Scale;^{165,166} 3) Psychological distress: anxiety and depression subscales of the Brief Symptom Inventory,¹⁶⁷⁻¹⁶⁹ Short Perceived Stress Scale;^{170,171} 4) Defensive Avoidance^{172,173}

CGRA Mode Preferences: At the 6-month follow-up, we will elicit their preferred mode of CGRA delivery (telephone, internet (Skype), or in-person) and reason for this preference.

Reactance to Intervention Materials: At the 1-month survey, participants will be asked if they received and read the print intervention materials (e.g., brochure, tailored letter, reminder action plan) and had telephone coaching.⁵³ For those who respond "yes,"^{53,174-176} open-ended questions will also be included regarding what participants liked and did not like about the materials.

Future Research: At the 6 and 12 month surveys, participants will be asked if they are interested in participating in future research.

Cost Data Collection: For the economic assessment, we will collect data on: 1) cost of print materials and mailings; 2) health education specialist time to deliver the intervention and follow-up navigation; 3) participant out-of-pocket and time costs; 4) costs associated with the CGRA and genetic test (BRCA1/2 or gene panel test); and 5) overhead related to the intervention (space, etc.). Time will be valued at US wages rates using data from the US Bureau of Labor Statistics.¹⁷⁷ Some costs will obviously differ by study arm (e.g., telephone/internet charges and time), but other differences may be less obvious. Since we are interested in future replication costs, we will focus on intervention delivery costs, including events and health care use. Briefly, health education specialists will record time and resources used delivering the interventions on participant encounter forms; these forms will be compiled to calculate averages. Participants will be asked questions regarding how much time they spent, how much childcare they paid for, and how many miles they traveled for each preventive measure, cancer genetic risk assessment, or genetic test they report getting. We have successfully used these methods previously.^{54,178,179}

Table 5. Concordance Table of Measures

Measure	Base-line	1mo	6mo	12mo	Description
General Health and Clinical Information	x				Heath status, co-morbidity index, information on cancer diagnosis(es)

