CGRA Mode Preferences			x		At the 6-month follow-up, for those who have not had genetic counseling but desire it, we will elicit their preferred mode of CGRA delivery: telephone, internet (Skype), and in-person along with the reason underlying their preference.
Reactance to Intervention Evaluation Items adapted from previous work ^{41,53,173-175}		x			At the one month survey, participants will be asked if they received the print intervention materials and telephone health education specialist coaching from the GRACE Project. ⁵³ For those who responded "yes" to specific materials, a set of ^{174,175} participants will be asked open-ended questions regarding the materials. Participants will also report how much time they spent reviewing materials and speaking to a cancer education specialist.
Cancer Education Specialist Follow Up			x	x	Participants will report how long they spoke on the phone during follow up calls with the cancer education specialist.

Future online adaptations		x			Following intervention, internet usage and willingness to search for genetic service information will be assessed.
Cost Data			x	x	Several items will be used to conduct a cost analysis

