4.3 Subject Randomization

NJSCR will not be involved in the randomization process. Briefly, the Principal Investigator ([name]) will randomize consenting women to one of 3 intervention arms using block randomization – (1) Usual care, (2) Mailed Targeted Print, and (3) Telephone Counseling and Navigation. Randomization will be single blinded. Research team members who are assessing the outcomes will be blinded to study arm assignment. Research staff who are conducting follow-up interviews will be blinded to group assignment as much as possible. At the beginning of the follow-up interviews, the interviewer will request that the participant does not reveal the study arm they were assigned to.

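### The study's own survey items weaken interviewer blinding: the 1-month questions reveal all three arms, and the 6- and 12-month call-time item can reveal some TCN women

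*Protocol*

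**What the plan says.** Protocol section 4.3 makes two separate blinding statements. For outcome assessors it is unqualified: "Research team members who are assessing the outcomes will be blinded to study arm assignment". For interviewers it is qualified: "Research staff who are conducting follow-up interviews will be blinded to group assignment as much as possible". The only safeguard it describes inside the interview is that "the interviewer will request that the participant does not reveal the study arm they were assigned to".

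Section 1.8.B then sets out what is asked:

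- **1 month, text:** "At the 1-month survey, participants will be asked if they received and read the print intervention materials (e.g., brochure, tailored letter, reminder action plan"), and whether she had telephone coaching. Open questions on what she liked and disliked follow.
- **1 month, Table 5:** "participants will be asked if they received the print intervention materials and telephone health education specialist coaching from the GRACE Project". She also gives the time spent with the specialist.
- **6 and 12 months, Table 5:** "Participants will report how long they spoke on the phone during follow up calls with the cancer education specialist".

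CGRA status is asked at 1, 6 and 12 months. The primary outcome is CGRA by 6 months confirmed in the medical record, and confirmation starts from self-report: "Those reporting that they had CGRA will be asked to sign a medical release form so that we may verify their self-reported CGRA".

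**The concern.** Asking a woman not to say which arm she is in does little if the questionnaire goes on to ask what she received. The 1-month survey, which is the most revealing one, also collects CGRA intention, beliefs, knowledge, cancer worry, fear of hereditary cancer and distress. None of these has an external check. The SAP analyses 1-month intention as an outcome in its first item, and uses 1-month mediators in its first and third items. An interviewer who knows the arm could, without meaning to, prompt or record answers differently.

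For the primary endpoint the route is longer. Record review can remove a false report of CGRA, but it cannot recover CGRA that was never reported or for which no release was signed. If interviewers who know the arm probe or seek the release unequally, the arms would differ in the share of true CGRA that is verified.

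**Working it through.** **Step 1. What the items reveal.** Section 1.6 gives the arm contents. UC receives no intervention and TP is mailed the brochure. For TCN, "Prior to the telephone session, participants will receive the same brochure that the TP arm receives", and the call and tailored letter are TCN components only.

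| Answer | Arm implied |
|---|---|
| 1 month: no brochure, letter or coaching | UC |
| 1 month: brochure only | TP |
| 1 month: coaching or tailored letter | TCN |
| 6 or 12 months: some specialist call time | TCN |
| 6 or 12 months: no call time | UC, TP, or TCN without follow-up calls |

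If women recall and answer correctly, the 1-month items separate all three arms. The later item does not, because navigation calls are made only as needed and with the woman's permission (Table 3, steps 5 and 6).

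**Step 2. What is not stated.** The documents do not give item order, separate staff or self-completion for these items, or a rule on who interviews a woman at the next wave.

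**Step 3. What unequal capture could do.** The plan gives no figure on this point, so the capture rates below are assumptions. Let s be the share of true CGRA that is reported, released and verified. Verified uptake is p × s, with true uptake p of 19% in TP and 34% in TCN (section 6.1.B).

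- True: OR = (0.34/0.66)/(0.19/0.81) = 2.20; difference 15.0 points.
- s = 90% in both arms: 0.306 vs 0.171; OR = (0.306/0.694)/(0.171/0.829) = 2.14; difference 13.5 points.
- s = 90% TCN, 80% TP: 0.306 vs 0.152; OR = (0.306/0.694)/(0.152/0.848) = 2.46; difference 15.4 points.
- s = 80% TCN, 90% TP: 0.272 vs 0.171; OR = (0.272/0.728)/(0.171/0.829) = 1.81; difference 10.1 points.

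**Step 4. False positives under equal true uptake.** The inputs are 182 per arm and a two-sided likelihood ratio test at 0.025. The statistic is G = 2 Σ O ln(O/E), compared with chi-square on 1 degree of freedom, and rejection probabilities are summed over all binomial outcomes. As a check, for 19% vs 34% this gives power of 85.1%, and the pooled normal formula gives 84.5%, the protocol's figure. The table shows the rejection rate when true uptake is the same in both arms:

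| Capture in the two arms | Uptake 7% | Uptake 19% | Uptake 34% |
|---|---|---|---|
| 90% and 90% | 2.6% | 2.6% | 2.6% |
| 85% and 90% | 2.7% | 3.1% | 3.5% |
| 80% and 90% | 3.2% | 4.5% | 6.6% |
| 70% and 90% | 5.2% | 11.3% | 22.0% |

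A 5-point gap in capture hardly matters. A 20-point gap would.

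**The case against.** The strongest case on the other side has five parts.

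- **The promise is qualified.** Interviewers are to be blinded only as far as possible. That stands, so no absolute guarantee is broken. But the qualifier fits accidental disclosure better than a scripted question that could be placed or administered differently.
- **The questionnaire is not in view.** The protocol is the New Jersey recruitment application, and the surveys are built at the prime site. Table 5 lists the reactance and specialist-call rows near its end, which would fit a closing module. Table order is not survey order, so this leaves the matter open. Even if the items came last, an interviewer used again would know the arm at the next wave.
- **Other blinding is untouched.** Nothing shows that record reviewers or the biostatisticians learn the arm. That stands.
- **The SAP has sensitivity analyses.** The primary paper adds self-reported outcome and both negative and multiple imputation. The self-report analysis covers women who report CGRA but give no release. It does not cover unequal reporting, and it depends on the same interviews.
- **Participants know what they received.** Reporting could differ by arm even with fully blinded interviewers, so not all of an assumed capture gap can be put down to interviewer knowledge. That stands.

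A reader might infer that blinding is wholly undone and that the primary result is biased in favour of TCN. The documents do not support this. It would need the call-time item to precede the CGRA question and release request, or an interviewer who learned the arm at 1 month to return, and then unequal probing or release-seeking. None of these is shown.

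**Conclusion.** The point holds in a limited form. The 1-month items reveal UC, TP or TCN to whoever asks them, in the survey that also collects the intention, belief and emotion scales. The 6- and 12-month item can reveal some TCN women only. The stated safeguard of asking women not to disclose the arm is therefore defeated by the survey's own content, unless item order or staffing not described in these documents prevents it.

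Self-reported scales and self-reported CGRA are directly exposed. Record-verified CGRA is exposed only through who reports it and who signs a release. The effect on the primary odds ratio cannot be sized from the documents: the values of 1.81 and 2.46, against a true 2.20, rest on assumed capture rates and show only that either direction is possible. This is an inexpensive improvement worth making, not evidence that the primary result is wrong.

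**What to change.** At 1, 6 and 12 months, put the material-receipt, coaching, reactance and specialist-call items in a closing module. Open it only after CGRA and testing status, the release request and all scales are saved. Collect that module by self-completion or, where existing staffing allows, give the woman's next wave to a different interviewer. Amend section 4.3 to say so.

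The cost is a reordering of the REDCap forms and some scheduling. No new items or visits are needed, and the process and cost data are kept. The documents do not give interviewer numbers, so the different-interviewer route depends on staffing.

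The SAP is dated January 2025 and written in the past tense. If data collection is complete, reordering cannot help. In that case, restate the blinding claim to say that interviewers could learn the arm from the 1-month items. Report by arm how many women reported CGRA, how many signed a release and how many were verified, together with the item order used and whether interviewers were reused across waves.
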